#### 6. Completion of 6-Month Follow Up Survey (T3)

All participants who have genetic testing will be asked to complete a T3 survey 6 months after the genetic testing result disclosure session (**Appendix J**).

## 7. Completion of 12-Month Follow Up Survey (T4)

All participants who have had genetic testing will be asked to complete a T4 survey 12 months after the genetic testing result disclosure session (**Appendix J**).

## OUTCOMES AND MEASURES

Table 1. Effectiveness outcomes and measures			
CONSTRUCT	T0	T1	T2-T4
Moderators of patient outcomes			
Sociodemographics	X		
Cancer history	X		
Family history	X		
Health literacy	X		
Comfort with technology	X		
Self-efficacy	X		
Financial Wellness	X		
COVID Impact	X		X
Outcomes			
Uptake counseling, testing, identification carriers at 6 months* (Telegenetics records for Arms A/B & the 6-Month Status Survey in Arm C)			
Understanding of Genetic Information**			
Test result recall			X
Knowledge of genetic disease	X	X	X
Perceived risk	X	X	X
Reactions to genetic information**			
Anxiety and Depression	X	X	X
Cancer specific distress	X	X	X
Satisfaction with genetic services and telemedicine		X	X
Behavioral use of genetic information**			
Performance of behaviors	X		X
Cost (patient and system)**		X	X

\*Aim 1; \*\*Aim 2; T0=baseline (within 30 days of visit 1, can accept within 45 days. beyond that it needs to be updated), waitlist usual care participants will need to complete a new baseline, T0b; T1=survey post pre-test counseling, Visit 1 (ideally collect 1-3 days and up to 7 days. accept up to 14 days but from 7-14 days we may elect to drop and impute). T2=survey immediately post genetic testing disclosure (same timing as T1); T3/T4 survey=6/12-month post genetic testing disclosure (ideally get within 14 days of 6/12 month mark but accept within 60 days of 6 month or 12 month mark)

The T0-T4 patient surveys for the RCT will be completed through a secure website, linked through the myLTFU platform. The 6-Month Outcome Survey will be administered by phone. If the phone survey cannot be completed, the survey will be offered self-administered through the myLTFU platform.

Effectiveness Outcomes (Aims 1 and 2):

**1) Uptake of counseling, testing and identification of carriers at 6 months** (Aim 1): This information will be obtained through study records for Arms A and B (intervention arms) and the 6-Month Outcome Survey among nonresponders in Arm A and B (e.g. those who did not contact Penn Telegenetics or did not complete visit 1 or visit 2) and in Arm C (usual care). The outcome survey will query completion of each outcome, date, and provider and will explore barriers and reasons for no uptake (Appendix I).

**2) Understanding of genetic information** will be assessed at baseline (T0, all Arms), post genetic pre-test counseling session (T1), post genetic test (T2), 6 months post genetic testing (T3), and 12 months post genetic testing (T4) for those in Telegenetic Arms A and B.

*Knowledge of genetic disease* will be evaluated using The KnowGene Scale, a 16-item scale administered to patients after genetic testing and/or genetic counseling to measure their understanding of the health implications of genetic testing results. It includes health implications to oneself as well as relatives. This measure covers penetrance, actionability, limitations of current technology, and monogenic inheritance patterns (51).

*Perception of genetic disease* will include three items (T0-T4), utilized in related research and evaluating perceived risk of developing a second cancer on a verbal scale and perceived numerical risk, as well as a single item evaluating perceived timeline. (52, 53, 54, 55) .

**3) Reactions to genetic information** will be assessed at baseline (T0, all Arms), post genetic pre-test counseling session (T1), post genetic test (T2), 6 months post genetic testing (T3), and 12 months post genetic testing (T4) for those in Telegenetic Arms A and B.

- a) General anxiety and Depression will be assessed by the 4-item each short Patient Reported Outcomes Measurement Information System (PROMIS), a system of highly reliable, precise measures of patient-reported health status for physical, mental, and social well-being (56, 57).
- b) Disease-specific distress will be measured using the 8 -item Impact of Events Scale (IES) (58-61), also with strong internal consistency ( $\alpha = 0.82-0.90$ ) in genetic delivery studies (62-64).
- c) Satisfaction with genetic services will be assessed with 9-items evaluating satisfaction with genetic services (T1 and T2). These items have been utilized in our related studies evaluating alternative and traditional genetic delivery models ( $\alpha = 0.73-0.85$ ) (62, 63, 65-69) and adapted for web-based delivery and this study design.
- d) Satisfaction with telemedicine will be assessed with 8-items adapted for genetic counseling sessions and utilized in our preliminary studies.(70)
- e) Multidimensional responses to genetic testing, including positive responses and uncertainty will be assessed using the Multi-dimensional Impact of Cancer Risk Assessment Questionnaire (MICRA) at T2-T4. The MICRA is a 21-items scale that has been utilized in many genetic studies to evaluate distress, uncertainty and positive

responses to receipt of genetic test results (71). The final item was excluded as it is not included in the three subscales and assessed regret which will be assessed in a separate scale.

f) Decisional regret (T2-T4) will be assessed with the 5-item validated Decision Regret Scale used frequently in related genetic studies (72, 73).

**4) Use of genetic information** will include performance of behavior items utilized in the CCSS and related studies (T0, T3, T4). Behaviors will include cancer specific (screening, prophylactic surgery, chemoprevention) and general risk modifying behaviors (e.g. diet, exercise, tobacco and alcohol use). Communication with providers and relatives following disclosure will be measured as well.

**5) Cost of remote services and usual care:** Estimation of intervention costs will adopt a societal perspective, including relevant direct medical and nonmedical costs borne by providers, payers and patients. These include print materials, postage, telecommunication services and personnel time required to deliver each intervention, as well as patient time and travel costs associated with genetic counseling sessions. Information to estimate intervention costs will be collected from study billing and payment records (e.g. print materials, postage) and telegenetic staff logs (personnel time). The cost of personnel time will be based on institution-specific salaries, including fringe benefits, for the personnel delivering the study interventions. In sensitivity analysis, we will substitute site-specific salary information with national average wage rates for the relevant occupational categories (e.g. physician, genetic counselor, office assistant). Intervention cost estimates will not include the cost of resources used solely for research purposes. Information about patient time and travel and other out-of-pocket costs (e.g. co- payments), will be obtained through the participant surveys. If patients report utilizing other health care services as a result of their study participation (e.g. additional medical or counseling visits) within the 6-month follow-up period, these services will also be included as immediate downstream costs of the interventions. Service unit cost values will be based on values reported in the literature or Medicare fee schedules. Medicare's reimbursement methodology was developed to approximate true resource costs. Thus, Medicare reimbursement amounts are appropriate for this purpose, even though we expect few participants will be covered by Medicare. Cost/service use will be assessed at T1, T2, T3 and T4 timepoints.

***Moderators of patient outcomes with remote telegenetic services (Aim 2b): Moderators*** (T0 only) include sociodemographics, health literacy and comfort with technology.

- a) Sociodemographic data will include race/ethnicity, education, marital status, gender, age, employment status, household income, health insurance (yes/no) and a usual source of medical care (yes/no) which will be collected in the Baseline Survey (T0)
- b) History of cancer will be collected in the Baseline Survey (T0).
- c) Genetic test result (positive, negative, true negative and test/genes included) will be obtained from Telegenetic Service records and the 6-Month Outcome Survey.
- d) Health literacy will be assessed at baseline (T0) with 3 health literacy Brief Literacy Screen (BHLS) screening items which have been validated to detect inadequate health literacy in clinical medical populations (74).
- e) Computer literacy will be assessed at baseline (T0) with selected items from the NCI Health Information National Trends Survey (HINTS), including internet and social media use (8 items), electronic medical record use and perceptions of privacy (14

items).(78)

- f) Self-Efficacy will be measured at baseline (T0) with the 4-item PROMIS Self-efficacy short form for managing chronic conditions, which has been validated in adults with medical conditions (including cancer) and has good internal consistency (alpha= 0.85-0.92).(77)
- g) Financial wellness will be measure at baseline (T0) with 2 items from the Personal Financial Wellness Scale. (91)
- h) Psychological impacts due to COVID-19 will be assessed using 15-16 items previously utilized in the CCSS to assess the impact of the COVID-19 pandemic on CCSs. The final item asking about number of individuals in the household is excluded at T2. While this protocol is independent of COVID-19, there is potential for COVID-19 events and impact on psychosocial outcomes to impact other primary and secondary outcomes. The measure is included to allow for analyses to evaluate the impact of these on study outcomes (78)

**Implementation outcomes (Aim 3):** CFIR informed constructs have been selected to evaluate factors related to uptake of remote telegenetic services, implementation facilitators and barriers and adaptations. We will collect quantitative and qualitative data from multiple key informants (e.g. patients, PCPs, office staff, PCP advisory board and research staff.) Additional methods and analyses included in **Appendix K:** Reporting and analysis plan for implementation outcomes.

### 3.4 Duration of Protocol

We anticipate the total enrollment for this protocol will last no longer than 5 years.

### 3.5 Location where research will be conducted

This research will be conducted at the University of Pennsylvania, the University of Chicago and at the CCSS Coordinating Center at St Jude.

### 3.6 Number of experimental subjects

An approximate 520 participants are anticipated to enroll to meet enrollment goals for the randomized trial (both Aims 1 and 2). As outlined above, once enrollment goals for Aim 1 are reached (120 completed baseline survey and sent randomization flyer), we will halt enrollment of Arm C. We will continue to enroll to Arms A and B to meet enrollment goals for Aim 2.

An approximate 15-30 patients, 15-30 primary providers and 15-30 primary care provider office staff participants are anticipated to enroll for aim 3, for a total of up to 90 additional participants (**Appendix K**).

## 4.0 Statistical Considerations and Analyses

**Analyses for Aim 1:** *We hypothesize that patients randomized to remote telegenetic services will have significantly higher uptake of the composite variable denoting genetic testing or genetic counseling at 6 months.* Our primary outcome will be a composite variable of whether the person had genetic testing or genetic counseling by 6 months (1 if either is true, 0 if neither is true). Uptake of separate genetic testing or genetic counseling decisions (as some patients will make informed decisions to defer testing) and identification of genetic carriers will be three secondary outcomes. We will use Fisher's Exact tests to compare uptake of our primary composite variable and secondary outcomes between the arms. The primary comparison groups will be the usual care/waitlist group vs. the combined remote telegenetics groups (phone

plus videoconference) prior to rerandomization of the waitlist group. For the primary analyses, we will use an intention to treat approach whereby comparisons are made between randomization arms. In secondary analyses, we will compare the randomization arms to investigate if potential confounders (e.g. age) are balanced among the randomization arms. We will do this via pairwise Wilcoxon-rank sum tests and Chi-squared tests as appropriate. If any potential confounders are not found to be balanced among the randomization arms (i.e.  $p < 0.10$  for any potential confounders in pairwise comparisons), we will use multiple logistic regressions of uptake to investigate the randomization arm effect. In these models, we will include randomization arms as binary (0/1) indicator covariates (leaving one out as the reference); we will also include the potential confounders as covariates in the regressions. These regression models will be akin to sensitivity analyses, designed to study if our inferences are robust after accounting for potential confounders.

**Missing data:** We do not expect substantial missing data, although there may be loss to follow-up over time. For the primary outcomes, we will assume that those lost to follow-up did not have pre-test counseling or testing (i.e. failures under the intention-to-treat paradigm). Data from our community practice stakeholder interviews suggests this is reasonable since many patients do not get genetic services even when referred. In secondary analyses, we will account for missing data using the multiple imputation technique of Raghunathan with 25 imputed datasets.(81) We will contrast the results obtained through imputation and those obtained from complete case analyses to study if missing data bias could be substantially affecting our inferences.

**Sample Size Justification for Aim 1:** We chose our sample size to have sufficient power for both Aims 1 and 2. For Aim 1, the sample size was selected to detect average differences in the primary endpoint (a composite variable indicating either genetic testing or genetic counseling) between the primary randomization arms of interest. The primary comparison groups will be the usual care/waitlist group versus the combined remote telegenetics groups (phone or video conference as one group); the primary analysis will consider the groups prior to the waitlist rerandomization. Preliminary data demonstrated that uptake of genetic testing from an ongoing registered randomized trial of remote telegenetic services vs. usual care for cancer genetic testing in community practices was at least 53% (29/55 with uptake) in the intervention arm, but only 17% (4/24 with uptake) in the control arm. With 120 patients in the usual care/waitlist group and 240 patients in the combined telegenetics groups with complete data (after accounting for loss to follow up), we will have  $>99\%$  power to detect a similar difference in uptake of genetic testing. This assumes a 1% Type I error rate (2-sided) and the use of Fisher's Exact Test. We set the Type I error rate to a conservative 1% to partially account for multiple hypothesis testing when including secondary outcomes and potential moderators in Aim 3. Given the magnitude of the pilot data differences, we anticipate excellent power for the moderator/subgroup analyses. The comparison of the usual care/waitlist group to the combined telegenetics group will be the comparison used to determine if the study accomplishes its primary objective. The uptake of pre-test counseling (Aim 1 secondary objective) and comparison between the phone and videoconference groups (see Aim 2a) are secondary objectives.

**Analyses for Aim 2:** *We hypothesize that remote telegenetic services by videoconferencing will be associated with greater decreases in cancer related distress and depression and increases in knowledge when compared to phone services.* Our primary outcomes for Aim 2a include changes in 1) cancer related distress; 2) depression; and 3) knowledge. We will compare the usual care at baseline group to the combined arms receiving remote services at baseline. For

comparisons between the remote videoconferencing versus phone groups, we will assign participants to the remote group assigned at baseline, or after rerandomization for the waitlist group. Our primary change scores for the first three variables will be change between baseline and immediately post genetic testing. For the waitlist group, there will be a second baseline measurement after the usual care period has ended. For the 3 primary analyses in Aim 2, we will use T-tests. We will assess balance of potential confounders (e.g. age, race, study site, waitlist assignment) between arms using T-tests or Fisher's exact tests as appropriate. Waitlist group will be considered a confounder in these secondary regression analyses. We will use multiple linear regression models to control for potential confounders inadequately balanced. We will include in the models the confounding variables and indicator (binary 0/1 variables) to indicate randomization arms (leaving one group out as the reference). For longitudinal analyses, we will examine time trajectories using regressions estimated by Generalized Estimating Equations (GEE) to account for within subject temporal correlation. Panel time will be included via indicator variables. We will also include interaction terms between randomization arm and time indicators to investigate temporal effects.(82) We will repeat analyses, but assign participants to per-protocol (i.e. restricting sample to those who properly used the assigned method of disclosure) or as-treated groups (e.g. assigning all participants to a group based on the method of disclosure used, regardless of assignment). For Aim 2 secondary outcomes, we will use multiple linear regressions for continuous outcomes and multiple logistic regressions for binary outcomes using GEE-estimation as described.

To evaluate moderators of patient cognitive, affective and behavioral outcomes (Aim 2b), we will use logistic regressions in which we include variables of interest as covariates. For moderation (i.e. effect modifier analyses), we will include indicator variables for randomization arms in the GEE-estimated multiple linear (for continuous outcomes) or logistic regressions (for uptake); we will also include panel time indicators, the potential moderator variables, and all two-way and three-way interactions among the arm/time/moderator variables. Interactions are created by multiplying two variables together.(82) To maintain power, we will examine non-time moderators separately. We will also examine multiple regression models with potential confounding variables. We will repeat the analyses but assign participants to per-protocol (i.e. restricting sample to those who properly used the method of disclosure as assigned) or as-treated groups (e.g. assigning all participants to a group based on the method of disclosure used, regardless of group assignment).

The economic impact of remote telegenetic services (Aim 2c) will be assessed by performing: 1) cost analysis and 2) cost-effectiveness analysis. The goal of the cost analysis is to estimate the cost of delivering remote telegenetic services, by phone and videoconference, compared to usual care. As above, the cost analysis will take a societal perspective, including the costs of all resources consumed for the implementation and delivery of remote genetic services.

Separately, we will examine costs from the health system perspective that can inform decisions about the provision and reimbursement of services, and ultimately will influence the effective dissemination and implementation of remote telegenetic services beyond the study. Cost-effectiveness will be estimated as the incremental cost per (1) additional survivor who receives genetic testing, and (2) additional mutations detected. The numerator of the incremental cost-effectiveness ratio (ICER) will include intervention costs and patient time and travel costs, estimated as described above. In the first analysis, the denominator will be defined by the primary trial endpoint of genetic testing received within 6 months. Because receipt of genetic testing is the measure of effectiveness in this case (i.e. the denominator of the ICER), neither the cost of testing nor the cost of related services provided after genetic testing will be included in the numerator. For the second analysis, the numerator of the ICER will include both genetic test costs and any related health care service costs (additional tests, visits, counseling)

associated with genetic testing at 6 months. Incremental cost effectiveness will be estimated using standard methods, and sensitivity analysis will be used to assess the impact of assumptions and uncertainty on results and conclusions.(83, 84) Although estimation of lifetime costs and outcomes associated with remote telegenetic testing is beyond the scope of this proposal, our results could serve as preliminary data for future grants that explore the long-term cost-effectiveness of increasing genetic testing among cancer survivors.

**Sample Size Justification for Aim 2:** We further chose our sample size such that we would have sufficient power for Aim 2 comparisons of the videoconference versus phone arms. After rerandomization of the waitlist group, we anticipate potentially having 180 people/arm randomized to the videoconference or phone arms. Based on prior experience, we anticipate that loss to follow-up will be less than 28% in each arm, leaving us with 130 evaluable participants with follow-up data in each group ( $180 - 180 \times 0.28 = \text{approximately } 130$ ). Some of the loss to follow-up will occur prior to the waitlist group being rerandomized. We used our pilot data to determine power for this aim (see Table 2 for estimates). We assumed 85% power and a 1.67% Type I error rate. We used a 1.67% Type 1 error rate (2-sided) by applying a Bonferroni correction for the three outcomes of interest to the typical 5% Type I error rate ( $5\% / 3 = 1.67\%$ ). We see in Table 2 that we have excellent power for all three arms with at least 95/arm, which is well below our expected 130/arm anticipated sample size. Table 2 also demonstrates that we have sufficient power for subgroup analyses, with a sample size of just 22/arm needed for knowledge comparisons between arms.

Table 2. Sample size calculations for Aim 2		
Variable	Change scores + (SD) of phone vs. videoconferencing	Number needed*
Knowledge	+5.7 (11.2) vs. +18.6 (12.6)	22/arm
Cancer specific distress**	+3.6 (12.4) v. -2.6 (12.3)	95/arm
Depression	-0.2 (2.0) vs. -1.6 (2.0)	50/arm

+Baseline to post genetic testing \*85% Power, 1.67% alpha; \*\*intrusive subscale

Amendment note added June 5, 2023: Our anticipated visit 2 completion sample size for the phone and videoconferencing arms will be 60 to 80 per arm, which is below are initial goal of 180/arm. With 60 to 80 per arm, we will still have adequate power for the knowledge and depression endpoints.

Analyses for Aim 3 included in **Appendix K**.

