##### 1. Randomization

Upon successful completion of informed consent and baseline (T0) survey, participants will be randomized into one of three potential study arms. Randomization assignments will be determined by a permuted block design and stratified by male/female/other. Study arms will consist of variations of methods of delivery for genetic counseling.

Once enrollment goals for Aim 1 are reached (120 completed baseline survey and sent randomization flyer), we will halt enrollment of Arm C. We will continue to enroll to Arms A and B to meet enrollment goals for Aim 2.

ARM	COUNSELING METHOD
ARM A	Remote Videoconference Telegenetics
ARM B	Remote Phone Telegenetics
ARM C	Usual Care

After randomization, participants will be sent information flyers (**Appendix E**) via the myLTU app that correspond to the appropriate arm to which they have been randomized. Flyers will include instructions for how to contact the Penn Telegenetics team to schedule their appointment (Arms A and B) or usual care options (Arm C) for obtaining genetic services (e.g. ask PCP or providers, use the National Society of Genetic Counselors website [www.nsgc.org](http://www.nsgc.org)).

Participants will be followed up with by a member of the research team to ensure they have received the flyers with the randomization assignment and information. Participants in all arms will be fully informed of how to initiate genetic services, and that it is their responsibility to do so.

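### The secondary adjusted models for Aims 1 and 2a depend on baseline balance tests, so chance decides whether the Aim 1 model is run and which covariates enter the Aim 2a models

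*Combined protocol and SAP*

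**What the plan says.** **Aim 1 (section 4.0, Analyses for Aim 1).** The primary analysis is unadjusted: "We will use Fisher's Exact tests to compare uptake of our primary composite variable and secondary outcomes between the arms". Potential confounders are then compared between arms, pair by pair. The condition for adjustment is "If any potential confounders are not found to be balanced among the randomization arms", defined as p<0.10 in any pairwise comparison. Only then is a logistic regression of uptake fitted, and the plan treats it much like a sensitivity analysis. Age is the only confounder named, as an example. The text does not say whether all potential confounders enter once one is flagged, or only those flagged.

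**Aim 2a (section 4.0, Analyses for Aim 2).** The three primary comparisons are t-tests on change scores. For the secondary models: "We will use multiple linear regression models to control for potential confounders inadequately balanced". No p-value threshold is given. Age, race, study site and waitlist assignment are examples of what is checked, and waitlist group is separately declared a confounder.

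**Randomisation (section 3.3, item 1).** "Randomization assignments will be determined by a permuted block design and stratified by male/female/other". Neither the Aim 1 nor the Aim 2a treatment-effect analyses name this stratum, and the baseline score is not named as a covariate for Aim 2a. Gender does appear in section 3.3 among the sociodemographic moderators for Aim 2b.

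**The concern.** When the arms being compared were randomised over the same period, a baseline difference between them is a chance difference. A small balance p-value shows that this draw was uneven on that variable. It does not show that the variable predicts uptake, distress, depression or knowledge. A rule built on it can leave out a strong predictor that happens to be balanced and let in an irrelevant one that is not.

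The Aim 1 regression is meant to show whether the inference is robust. A robustness check whose existence depends on a chance event, and whose covariates are not listed, cannot be stated before the data are seen and is weak support. In Aim 2a the rule works on the content of the model: the covariates that enter are those that happened to differ.

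The stratum fares worst under such a rule. Stratified blocking keeps it balanced, so a balance test will almost never select it, although it is the one variable the design itself treated as worth controlling.

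**Working it through.** **1. The plan's own Aim 1 power.** Section 4.0 gives the inputs: "With 120 patients in the usual care/waitlist group and 240 patients in the combined telegenetics groups with complete data"; uptake that "was at least 53% (29/55 with uptake) in the intervention arm, but only 17% (4/24 with uptake) in the control arm"; and "This assumes a 1% Type I error rate (2-sided) and the use of Fisher's Exact Test". Full enumeration of the two-sided Fisher test with 120 versus 240, 4/24 = 16.7% versus 29/55 = 52.7% and alpha 0.01 gives power of 99.9996%. The stated figure above 99% reproduces, and nothing below alters it.

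**2. How often one Aim 1 covariate triggers adjustment.** Three arms give three pairwise tests, each at p<0.10 (|z| > 1.645). Simulation under correct randomisation (200,000 replicates) gives P(at least one of three flagged) = 0.225 with 120/120/120 and 0.225 with 200/200/120. This is below 1 − 0.9³ = 0.271 because the three tests share arms. The probability is the same whatever the covariate's prognostic value.

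**3. How often the Aim 1 model is triggered.** With k independent covariates, P(at least one flag) = 1 − (1 − 0.225)^k.

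| k | P(at least one flag) |
|---|---|
| 5 | 0.72 |
| 8 | 0.87 |
| 10 | 0.92 |
| 12 | 0.95 |

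The documents do not fix k. Eight is an assumption: section 3.3 lists nine sociodemographic items, and gender is removed because blocking balances it. Independence is also an assumption. Income, education, employment and insurance are likely to be correlated, which lowers the figure.

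**4. Aim 2a.** The phone-versus-video contrast has one comparison per covariate and no stated threshold, so the figures in steps 2 and 3 do not carry over.

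**5. Whether the rule would pick up the stratum.** In 5,000 simulated stratified permuted-block allocations of 360 people (block size 6 and a 50/50 male/female split assumed), the stratum was flagged in 0.

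**6. What omitting the stratum costs in Aim 1.** Assume two equal strata and mean uptake of 30%. If uptake differs by 20 points (20% versus 40%), within-stratum variance is (0.2×0.8 + 0.4×0.6)/2 = 0.20, against a total of 0.3×0.7 = 0.21, a ratio of 95.2%. For 10 and 30 points the ratios are 98.8% and 89.3%. Ignoring the stratum is mildly conservative and immaterial at this power.

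**7. Where precision matters: distress in Aim 2a.** Table 2 gives a difference of 3.6 − (−2.6) = 6.2 and SDs of 12.4 and 12.3. The pooled SD is √((12.4² + 12.3²)/2) = 12.35, and alpha is 0.05/3. The noncentral t with noncentrality 6.2/(12.35·√(2/n)) gives 85% power at n = 95, which reproduces Table 2. The June 2023 note expects 60 to 80 per arm. If fixed covariates explained a share R² of change-score variance (assumed), the SD would be multiplied by √(1 − R²).

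| n per arm | R² = 0 | R² = 0.10 | R² = 0.20 |
|---|---|---|---|
| 60 | 63% | 68% | 74% |
| 80 | 77% | 82% | 87% |

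**The case against.** The best defence is that nothing decisive depends on these models. The Fisher test and the three t-tests are specified in advance and unadjusted. The Aim 1 regression is presented as a sensitivity analysis and the Aim 2a regressions as secondary. That stands. A reader might infer that the primary conclusions are exposed to data-driven covariate selection, and the documents do not support that.

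Other points on that side also stand:

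- **Aim 1 model content.** A reader might conclude that the Aim 1 covariate set is picked by chance. The text can be read as entering all potential confounders once any one is flagged. On that reading chance decides only whether the model is run. The list is still unspecified, so the fix is the same.
- **The stratum.** It would be too strong to say that it appears in no analysis. Gender is an Aim 2b moderator, and the Aim 2b models with confounders carry no balance condition.
- **Waitlist origin.** The plan already calls it a confounder in the Aim 2 secondary regressions.
- **Precision in Aim 1.** Adding prognostic covariates to a logistic model does not shrink the standard error of the log odds ratio, and power is already above 99%. The Aim 1 argument is about prespecification.

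One further point is that Aim 2a uses people who reached result disclosure, a subset formed after randomisation, so imbalance there may not be pure chance. This does not rescue the rule: with 60 to 80 per arm, a non-significant balance test does not show comparability.

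**Conclusion.** The point holds for the secondary and sensitivity models of Aims 1 and 2a, and only for those. In Aim 1, chance decides whether the robustness model is fitted and, on one reading, what it contains. In Aim 2a, balance decides which covariates enter. Neither set of treatment-effect analyses names the stratum, and Aim 2a adjustment does not name the baseline score.

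The size for Aim 1 is about 0.22 per covariate, and about 87% for at least one of eight if the number and independence assumed are right. A reader might carry the 87%, or the p<0.10 threshold itself, over to Aim 2. The documents state that threshold only for Aim 1, so neither transfers.

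The practical gain is mainly in Aim 2a distress. Expected numbers fall short of the 95 per arm required, and unadjusted power is about 63% to 77% on Table 2's figures. A fixed adjusted analysis would give a more precise supporting estimate, by an amount that depends on the assumed R². This is a worthwhile and nearly free improvement, and it does not put the trial's main result in doubt.

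**What to change.** Remove the balance-test condition from both aims. Always fit the secondary adjusted models, with a short covariate list written into the SAP before the data are seen:

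- **Aim 1:** the male/female/other stratum, plus a few T0 covariates that the investigators judge prognostic for uptake (for example age and qualifying cancer or family-history group). The documents give no evidence on which variables predict uptake, so this choice is theirs.
- **Aim 2a:** the baseline score of the outcome (T0, or the second baseline for waitlist participants), the stratum and waitlist origin.

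Report baseline balance descriptively, without tests. Keep the Fisher test and the t-tests as the primary analyses.

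The cost is SAP wording and minor analysis work. The covariates come from T0 data, the second baseline already planned for the waitlist group, and randomisation records.
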